6.4.2 Germany

German Government Health Insurance (*Gesetzliche Krankenversicherung* [GKV]) claims from approximately 8-10 different statutory health insurance providers (SHIs) are collected by Team Gesundheit. This is an established research institute which has been working for more than 1000 health insurance companies, companies and ministries since 1997. With branches in Essen, Hamburg, Bielefeld, Berlin, Frankfurt and Munich they are active in German health management nationwide. Since an SHI is a requirement for individuals with a permanent place of residence in Germany, even for short-term stays, the general population coverage in the SHI is considered nationwide. The SHIs also allow insurance coverage for children and spouses within a family insurance policy. The population size available through Team Gesundheit is approximately 5 million individuals which represents an estimated 6.9% of the SHI-insured population in Germany. Available data history through collaboration with Team Gesundheit reaches back to January 2008. Since 2012 all individuals in Germany have lifelong specific ID and SHI numbers which would not change throughout lifetime.

The database contains information from primary care, in- and out-patient hospital care as well as sick leaves. Relevant measures are available in the German database allowing demographic characteristics, treatments, healthcare utilization and clinical outcomes to be assessed, for example:

- registration data including age, gender;
- out-patient care data including ICD-10 diagnoses (not granular and per quarter), physician specialty
- inpatient care claim including ICD-10 diagnoses (up to 3 principal and 30 secondary diagnoses per stay), billed diagnosis-related group (German classification), up to 30 OPS-Codes per stay, duration of hospitalizations, and medical department; drug prescription data including ATC codes of prescribed medications

Diagnosis information is available and captured in the ICD-10 coding system with German modification (GM). Data on surgical and medical procedures is recorded using operation and procedure classification system (OPS) codes which is the GM of the international classification of procedures in medicine (ICPM). Due to the nature of the claims data, information on data that is not subject to reimbursement is not visible in the database, e.g., information on symptoms captured by ICD-10 coding would have little or no coverage as they are usually not subject to reimbursement. Similarly, information on a conducted diagnostic test is only available if being subject to reimbursement. Test results are not available from the claims data. The estimated lag time from the time data is recorded until it is available for research is currently 16 months meaning that data until the end of 2022 would be available in March/April 2024. SHI data in Germany is updated yearly.

6.4.3 Spain

The Information System for Research in Primary Care (*Sistema d'Informació per al Desenvolupament de la Investigació en Atenció Primària* [SIDIAP]), IDIAP Jordi Gol (Spain) is a primary care records database that covers approximately 7 million people, equivalent to an 80% of the population of Catalonia, North-East Spain. SIDIAP is collected from EHR records of patients receiving primary care delivered through Primary Care Teams (PCT), consisting of general practitioners, nurses and non-clinical staff. The Catalan Health Institute manages 286 out of 370 such PCT with a coverage of 5.6 million patients, out of 7.8 million people in the Catalan population (74%). The database started to collect data in 2006. The mean follow-up is 10 years. The observation period for a patient can be the start of the database (2006), or when a person is assigned to a Catalan Health Institute primary care center. Date of exit can be when a person is transferred-out to a primary care center that does not pertain to the Catalan Health Institute, or date of death, or date of end of follow-up in the database. Drug information is available from prescriptions and from dispensing records in pharmacies. Studies using SIDIAP data require previous approval by both a Scientific and an Ethics Committee (20). For a subset of patients included in the SIDIAP database, linkage to hospital data is available as obtained from the Catalan Institute of Health hospitals (21) and will be further explored in the feasibility assessment. Healthcare is universal and taxpayer funded in the region, and primary care physicians are gatekeepers for all care and responsible for repeat prescriptions. SIDIAP-Hospitalization Linked Data has contributed to studies involving patients with MS (21).

6.4.4 Italy

The Italian Multiple Sclerosis & Related Disorders Register (*Registro Italiano Sclerosi Multipla e Patologie Correlate* [RISM]) was officially established in 2015. As of February 2023, the register was actively covering 133 MS centers, corresponding to a total of 80,353 patients, of which 273 are diagnosed with NMOSD. Since July 2022, the

register comprises a module for the collection of information on NMOSD, and has projects dedicated to NMOSD patients (22). Nonetheless, data on NMOSD patients were collected previous to 2022, without a specific module implemented. The data are collected from participating centers through a web-based system developed for the study, available at the IMS&RD website. Data are collected from accrual to exit of database, which may occur at date of death, when patient moves to a center outside of the covered network or withdraws their consent to participate. The data are centrally monitored to ensure quality of data, completeness, accuracy, and consistence (23). Requests to access the data are evaluated by the Scientific Committee, composed by clinicians, methodologists, representatives of MS centers, and of the Italian Neurological Society (23).

To ensure the collection of sufficient data for the clinical characterization of the single patient mandatory variables collected by the register include patient identification, demographics, vital status, disease onset date, diagnosis date, relapses, treatments and severe adverse events. This minimum dataset may be completed with an extension to optional information on family history, comorbidities, laboratory tests and MRI. Furthermore, the register has data on patient's unique personal identifier, to avoid inclusion of the same patient by more than 1 center. Diagnosis information is available and captured with ICD-9-CM coding system.

6.4.5 The Netherlands

Established in 1998, the Dutch Institute for Drug Outcomes Research (PHARMO) Database Network is a population-based network of electronic healthcare databases and combines anonymous data from different primary and secondary healthcare settings in the Netherlands. These different data sources, including data from general practices, in- and out-patient pharmacies, clinical laboratories, hospitals, the cancer registry, pathology registry and perinatal registry, are linked on a patient level through validated algorithms. To ensure the privacy of the data in the PHARMO Database Network, the collection, processing, linkage and anonymization of the data is performed by STIZON. STIZON is an independent, ISO/IEC 27001 certified foundation, which acts as a Trusted Third Party (TTP) between the data sources and the PHARMO Institute. Detailed information on the methodology and the validation of the used record linkage method can be found elsewhere (24).

The longitudinal nature of the PHARMO Database Network system enables to follow-up more than 10 million persons of a well-defined population in the Netherlands for an average of twelve years. Currently, the PHARMO Database Network covers over 7 million active persons out of 17 million inhabitants of the Netherlands. Data collection period, catchment area and overlap between linked data sources differs. Therefore, the final cohort size for any study will depend on the data sources included. As data sources are linked on an annual basis, the average lag time of the data is one year. All electronic patient records in the PHARMO Database Network include information on age, sex, socioeconomic status and mortality. Other information available is dependent on the data source.

General Practitioner Database

The General Practitioner Database comprises data from electronic patient records registered by GPs. The records include information on diagnoses and symptoms, laboratory test results, referrals to specialists and healthcare product/drug prescriptions. The prescription records include information on type of product, prescription date, strength, dosage regimen, quantity and route of administration. Drug prescriptions are

The Hospital Database comprises datasets containing information on hospital admissions, ambulatory consultations, and high budget impact medication. The Hospital Database is collected and maintained by the Dutch Hospital Data Foundation and comprises records from nearly all hospitals in the Netherlands. With permission from each hospital the data are linked for research purposes with the PHARMO Database Network via the TTP. For more information, please see www.dhd.nl. Permission on a project basis is needed to obtain these data.

Hospital Admissions

This dataset comprises hospital admissions lasting more than 24 hours and admissions for less than 24 hours for which a bed is required (i.e., inpatient records). The records include information on hospital admission and discharge dates, discharge diagnoses and procedures. Diagnoses are coded according to the WHO ICD and procedures are coded according to the Dutch Hospital Data Foundation registration system for procedures (27)

which links to the Dutch Healthcare Authority (*Nederlandse Zorgautoriteit*, NZa) declaration codes (28) and the Dutch Classification of Procedures (29). Currently, PHARMO has access to data from 1998 onwards and of over 80% of the hospitals.

Ambulatory Consultations

This dataset comprises all ambulatory consultations (i.e., out-patient records). The records include information on each contact, including date, diagnoses and procedures. Diagnoses are coded according to the WHO ICD and procedures are coded according to the Dutch Hospital Data Foundation registration system for procedures which link to the Dutch Healthcare Authority declaration codes and the Dutch Classification of Procedures. Currently, PHARMO has access to data from 2016 onwards and of over 50% of the hospitals.

High Budget Impact Medication

In the Netherlands high budget impact medication is dispensed through hospitals. The dataset comprises all dispensed high budget impact medication. This data is available for all patients identified in the ambulatory consultation dataset. The records include information on date of dispensing, type of medication, number of units, indication of use and prescriber. Drug dispensing are coded according to the Dutch Z-index code (30). Currently, PHARMO has access to data from 2017 onwards and of over 50% of the hospitals.

It is expected that inebilizumab will be indicated as ‘high-cost medicine’ by the Dutch Healthcare Authority and can only be dispensed through hospitals. If this new therapy will not be indicated as ‘high-cost medicine’ it may be found in the In-patient Pharmacy Database which comprises drug dispensing from the hospital pharmacy given during a hospitalization (or for which a bed is required, ie, most IV drugs). This data is available for a subset of the patients identified in the ambulatory consultation dataset.

Pathology Registry

The nationwide network and registry of histopathology and cytopathology in the Netherlands is maintained by the *Pathologisch-Anatomisch Landelijk Geautomatiseerd Archief* (PALGA) foundation and comprises excerpts of histological, cytological and autopsy examinations. For research purposes the data can be linked with the PHARMO Database Network via the TTP. Electronic records include a summary of the pathology report and the so-called PALGA diagnosis which is structured along 5 classification axes: topography, morphology, function, procedure and diseases. For more information, please see www.palga.nl

Permission on a project basis is needed from PHARMO as well as the PALGA foundation to obtain these data.

6.5 Study Size

This is a descriptive study that will identify and characterize the patients who are treated with inebilizumab. There is no *a priori* hypothesis testing and no prespecified requirement of sample sizes. The final study size will be determined by the length of study period and uptake of inebilizumab in the countries and population covered in the data sources. In order to comply with pharmacovigilance reporting commitments, multiple data extractions are planned for EU countries. Slow uptake may impact on the ability to meet the study objectives; in this instance the feasibility of study completion within the proposed time frame and need for further data extractions, should be open to re-evaluation.

For this observational study, the interpretation of results focuses on the precision of estimands (proportions). [Table 3](#) presents the sample sizes across a range of expected incidences (of patient characteristics or AESI) and levels of precision. The sample sizes are derived assuming a normal approximation for the 95% confidence intervals (CI). Thus, in this study a pooled cohort of 400 patients across data sources would enable a patient characteristic (or AESI) with an assumed incidence of 1% to be estimated with a precision of +/- 1%, and for a patient characteristic (or AESI) with an assumed incidence of 4% to be estimated with a precision of +/- 2%.

Table 3 Sample Sizes of Patients Required to Estimate the Expected (True) Cumulative Incidence of a Patient Characteristic or AESI With 95% Confidence Intervals of Different Precisions (0.2% to 5%)

Estimated Incidence (%)	Precision 0.20%	Precision 0.50%	Precision 1%	Precision 2%	Precision 3%
0.30	2 872	-	-	-	-
0.40	3 826	-	-	-	-
0.50	4 778	764	-	-	-
0.70	6 675	1 068	-	-	-
0.80	7 621	1 219	-	-	-
1.00	9 508	1 521	380	-	-
2.00	18 823	3 012	753	188	-
3.00	27 947	4 471	1 118	279	124
4.00	36 878	5 900	1 475	369	164
5.00	45 617	7 299	1 825	456	203

AESI, adverse events of special interest

Feasibility – Patient estimates

Data sources and study countries were selected following a high-level feasibility assessment. It addressed the appropriateness of data sources for completion of this study regarding the ability to identify the target population and the presence of some variables of interest (such as results for AQP4 testing).

Inebilizumab is recommended to patients with NMOSD and the expected number of patients identified with the disease may vary considerably due to the imprecision of the prevalence estimates. Considering countries’ population, data sources coverage, and expected NMOSD prevalence, the number of patients is likely to vary between 576 and 4,870 if 2006 NMO diagnosis criteria (31) were used for diagnosis; it may be higher depending on the criteria adopted in each setting. Around 80% of NMOSD are likely to be AQP4+ and thus eligible for inebilizumab, resulting in the identification of 461 to 3,896 patients (up to 8,855) ([Table 4](#)).

Table 4 Expected number of patients with a NMOSD diagnosis in each country (new and prevalent cases)

Country of Interest	Population ≥18 years	2006 NMO diagnosis criteria		2015 NMOSD diagnosis criteria
		Annual number of new cases (range) ^a	Number of patients with the disease (range) ^b	Number of patients with the disease (range) ^c
Germany ^d	5 000 000	(3-20)	(26-220)	(35-500)
Spain (Catalonia) ^d	5 600 000	(3-22)	(29-246) ^g	(39-560) ^g
Netherlands ^d	7 000 000	(4-28)	(36-308) ^h	(49-700) ^h
France ^e	53 179 816	(27-213)	(277-2 340)	(372-5 318)
Italy ^f	39 908 080	(20-160)	(208-1 756)	(279-3 991)
All countries	110 687 896	(57-443)	(576-4 870)	(774-11 069)
AQP4+ patientsⁱ	88 550 317	(46-354)	(461-3 896)	(619-8 855)

Abbreviations: AQP4, aquaporin-4 antibodies; NMOSD, neuromyelitis optica spectrum disorder

^aBased on an estimated incidence rate between 0.05 and 0.40 per 100.000 people (32)

^bBased on an estimated prevalence between 0.52 to 4.4 per 100.000 people (32)

^cBased on an estimated prevalence between 0.7 to 10 per 100.000 people (33)

^dData sources do not cover 100% population: Netherlands (PHARMO) is 7 million; Catalonia (*Sistema d'Informació per al Desenvolupament de la Investigació en Atenció Primària [SIDIAP]*) is 5.6 million and Germany (Gesetzliche Krankenversicherung [GKV]) is 5 million.

^eCoverage is around 100%, population on 1st January 2021 (34)

^fCoverage is around 80%, population on 1st January 2021 (34)

^gExpect between 50 to 150 patients, based on feasibility counts provided from the data source but considerable proportion based on ICD-10 code H46; no data available on AQP4-Ig results

^hExpect 50 patients in 2020, based on feasibility counts provided from the data source

ⁱAssuming 80% of NMOSD patients AQP4+ (4)

6.6 Data Management

6.6.1 Database Management

The processes for database management differ by country. Generally, the data is stored at the database level and analyzed in accordance with local policy. SAS, STATA or R language will be utilized for access to the raw data, to manage the analytic datasets and to conduct data analysis. If the study is conducted by a third party, the datasets and analytic programs will be stored according to the vendor's procedures. This study will follow the relevant chapters of the ENCePP and the International Conference on Harmonisation (ICH) guidelines for data management (27, 28)

6.7 Data Analyses

6.7.1 General Considerations

A generic description of the analysis methods proposed for this study is presented in [section 6.7.2](#) followed by a description of the analysis proposed for each specific objective of the study.

A global SAP will be developed to describe in full details the variable definitions for exposures, outcomes, covariates, and sub-groups of interest. All analytic methods will be detailed, and a full set of table shells will be included. The SAP will be developed after the final protocol approval.

Descriptive analysis will consist of the summary statistics for continuous and categorical variables. For continuous variables, the number of observations, number of missing values, mean, standard deviation, median, lower (1st) and upper (3rd) quartiles, as well as 5th and 95th percentiles will be presented. For categorical variables, the numbers and percentages of observations for each of the categories and numbers and percentages of missing values will be reported. Confidence intervals of 95% may be presented, if data allow. Only available data will be summarized.

All descriptive analyses will be undertaken by country/data source, and for specified outcomes, a meta-analysis may be performed if a sufficient number of events per data source is observed.

The respective data sources' small number masking rules will define the lower limit for the number of units that can be reported in the result tables. The small number masking rules vary by data sources, and for example, PHARMO has a limit of 5. The small number masking rules of the data sources will be considered when presenting the study results for the analysis and numbers lower than the limit will be masked in the result tables. Further details on the masking rules and their impact on the result tables will be provided in the SAP.

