6.4 Data Sources

The inclusion of a country/data source in the study was based on the evaluation of the following aspects:

- time of inebilizumab launch (focus on the initial countries to launch inebilizumab)
- availability of data required to meet the study objectives (i.e., exposure to inebilizumab and other disease modifying drugs, safety outcomes)
- data bases in which the number of exposed patients was relatively high
- data availability in the defined study period, after taking into account the lag time (time from data capture to data available in the system)

The evaluation of the last 3 aspects was carried out through a detailed qualitative feasibility assessment in 17 different data sources in 9 countries. Ultimately, 6 data sources from 5 European countries were included in the study (Figure 3 Data Sources Included).

Figure 3 Data Sources Included

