- Data sources relying on drug prescription/dispensation - and not administration - may result in exposure misclassification and bias in the treatment patterns characterization and time-to-event analyses. Additionally, reasons for treatment discontinuation, switching or augmentation are not possible to capture not allowing the documentation of changes in treatment.
- Some variables, such as drug dose, laboratory results of biomarkers and exams such as MRI may not be available in all data sources which will limit comparability and the ability of a more detailed characterization of inebilizumab users in those countries.
- Other variables, such as treatment indication, if not available in the data sources, will be based on pre-defined algorithms.
- The evaluation of drug safety using secondary databases does not allow for a causal assessment between inebilizumab exposure and the experienced outcome. NMOSD has been shown to be highly associated with other diseases including cancer (40). Additionally, an increased risk of malignancies or serious infections in NMOSD may be induced by the exposure to other immunosuppressive therapies (41,42). Please note, most malignancies have long latency periods in the absence of immunosuppression (43), and although immunosuppressive therapies possibly shorten the period (44), current study follow-up time may be too short (up to 1 year is the maximum) to identify some malignancies. Therefore, safety outcomes should be considered as signals of a possible safety concern of inebilizumab exposure.
- This study will capture safety outcomes that were serious enough to come to medical attention, which may underestimate the frequency of mild events. Additionally, misclassification is a possibility as it relies on the diagnosis codes. Identified serious infections, serious infusion related reactions or malignancies

represent a subgroup of all serious adverse events but for which the validity is expected to be higher.

- For some data sources, reporting of small numbers (e.g., <5) requires compliance with the local policies regarding data anonymization and the risk of patients' identification in observational research. For example, if a real value is 2, it may need to be presented as ≤ 4 in the results table. This may be a potential limitation for analyses that require stratification, such as the number of malignancies in a specific age groups. Furthermore, minimum and maximum values cannot be reported.

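### The precision stated for a pooled cohort of 400 is not assured: section 6.7.1 analyses each source separately and allows pooling only optionally, if each source has enough events

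*Protocol*

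**What the plan says.** Section 6.5 says the study has "no prespecified requirement of sample sizes" and tests no hypothesis, so the case for its size rests on precision. It states that "a pooled cohort of 400 patients across data sources would enable a patient characteristic (or AESI) with an assumed incidence of 1" per cent "to be estimated with a precision of +/- 1" per cent. The second worked case is "an assumed incidence of 4% to be estimated with a precision of +/- 2" per cent. The abstract repeats the 1% case only. On method, section 6.5 says: "The sample sizes are derived assuming a normal approximation for the 95% confidence intervals (CI").

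Section 6.7.1 sets the level of analysis. Every descriptive analysis is done by country or data source. The only stated way of combining sources is that, for specified outcomes, "a meta-analysis may be performed if a sufficient number of events per data source is observed". No threshold for a sufficient number is given. The same section applies each source's small-number masking rule when results are presented and gives a limit of 5 for PHARMO as an example. Section 6.9 illustrates the effect: "if a real value is 2, it may need to be presented as ≤ 4 in the results table".

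Sections 6.7.2 and 6.7.2.3 refer to the overall study population, including for the cumulative incidence of each AESI category, but do not say how sources are combined to form it.

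**The concern.** The precision statement belongs to an analysis that the plan does not commit to. A reader of section 6.5 or the abstract will expect a 1% AESI risk to be reported to within about one point. Under section 6.7.1 the assured output is a set of source-level estimates, each from a fraction of the 400.

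The pooling condition also works against its purpose. The rarer the event, the more a pooled estimate is needed and the less likely it is that every source has enough events to permit one. The smallest counts are also those most likely to be masked. Quantifying AESI incidence is Objective 3 of a safety study, so this affects a main result.

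A second, smaller matter is that the 1% figure rests on a normal approximation with 4 expected events.

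**Working it through.** **Inputs.** Section 6.5: n = 400 pooled; p = 1% with half-width d = 1 point; p = 4% with d = 2 points; two-sided 95%; normal (Wald) approximation. Table 4, lower range under the 2006 criteria: France 277, Italy 208, Netherlands 36, Spain 29, Germany 26, total 576.

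**1. The plan's own figures.** n = 1.96² × p(1−p) / d².
- p = 1%, d = 1 point: 380.3 (Table 3: 380).
- p = 4%, d = 2 points: 368.8 (Table 3: 369).
- Every other Table 3 cell reproduces to within one patient.
- At n = 400 the half-width 1.96 × √(p(1−p)/n) is 0.975 points at 1% and 1.92 points at 4%.

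The arithmetic is right under the disclosed formula.

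**2. The same formula at source level.** The protocol does not say how 400 users would divide. Assume the Table 4 shares, n = 400 × count/576 (the upper-range counts give practically the same split). At p = 1%:

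| Country | n | Expected events | P(no event) | Wald half-width (points) | Exact upper limit if 0 events |
|---|---|---|---|---|---|
| France | 192 | 1.92 | 14.5% | 1.4 | 1.9% |
| Italy | 144 | 1.44 | 23.5% | 1.6 | 2.5% |
| Netherlands | 25 | 0.25 | 77.8% | 3.9 | 13.7% |
| Spain | 20 | 0.20 | 81.8% | 4.3 | 16.8% |
| Germany | 18 | 0.18 | 83.5% | 4.6 | 18.5% |

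With an equal split of 80 per country, expected events are 0.8 and the half-width is 2.2 points. At p = 4%, 1.96 × √(0.04 × 0.96/n) runs from 2.8 points (n = 192) to 9.0 points (n = 18), and is 4.3 points at n = 80.

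**3. How often the pooling condition is met.** Take the most lenient reading, that one event per country is sufficient. The probability is the product of 1 − (1−p)ⁿ over the countries.
- 1%, Table 4 split: 0.855 × 0.765 × 0.222 × 0.182 × 0.165 = 0.4%.
- 1%, equal split: (1 − 0.99⁸⁰)⁵ = 0.5525⁵ = 5%.
- 4%, Table 4 split: about 19%.

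**4. Masking.** If a limit of 5 applied everywhere (the protocol gives it only for PHARMO), the chance of at least 5 events at 1% is 4.5% in France, 1.5% in Italy and practically nil in the other three.

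**5. The approximation, if the data are pooled.**
- 4/400: exact (Clopper-Pearson) 95% interval 0.27% to 2.54%, that is −0.73 and +1.54 points, half-width 1.13. Wilson: 0.39% to 2.54%.
- Exact coverage of the nominal 95% Wald interval at p = 1%: 90.7% at n = 400 and 88.8% at Table 3's n = 380.
- At an observed 1%, the exact upper limit comes within one point only between n = 700 (7 events, 2.05%) and n = 800 (8 events, 1.96%).
- 16/400: exact interval 2.30% to 6.41%, half-width 2.06. Wald coverage at p = 4% is 94.8%.
- 0/400: exact upper limit 1 − 0.025^(1/400) = 0.92%.

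**The case against.** The best defence is that pooling is already implied. Section 6.7.2 conducts all analyses for the overall study population, section 6.7.2.3 calculates each AESI risk in that population, and section 9.1 promises aggregate AESI results in the final report. The threshold for sufficient events is open and a statistical analysis plan is to follow. This stands in part. A reader might infer that no pooled AESI estimate would be produced, but the documents do not support that; they support only that one is not assured. The conditional meta-analysis is the only combining method stated, and if the overall study population does mean pooled data, it conflicts with section 6.7.1. The later plan can define a threshold, but a plan that keeps the condition cannot assure what section 6.5 states.

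Second, 400 is illustrative and 1% is one row of a table running from 0.3% to 5%. That is true, but these are the figures chosen to convey the study's precision, in section 6.5 and, for the 1% case, in the abstract.

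Third, the approximation is disclosed and serves planning only. That also stands. The protocol does not fix the interval method for the analysis, so the 90.7% coverage describes the planning interval, not a reported one. The exact half-width at 1% is only modestly wider (1.13 against 1). What remains is the asymmetry: +1.54 points on the side that matters for safety.

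Fourth, imprecision and masking are acknowledged in section 6.9. They are, but in general terms that do not correct the numerical claim.

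**Conclusion.** The point holds as an inconsistency between study size and analysis that should be fixed. The ±1 and ±2 points in section 6.5 describe a pooled analysis that section 6.7.1 leaves optional and conditional. At source level the 1% figure would be about ±1.4 to ±4.6 points on the Table 4 split, or ±2.2 on an equal split. At 1% the condition would be met in about 0.4% to 5% of studies even if one event per country were enough. If the data are pooled, the ±1 at 1% should read 0.27% to 2.54%. The 4% statement fails only on the pooling point.

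The country split is an assumption: Table 4 counts diagnoses, not inebilizumab users, and launch dates and study periods differ. The calculations use five countries, with France taken once, and binomial limits treat each patient as having at most one counted event.

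Two stronger readings are not supported. Table 3 is not miscalculated. Nor does the protocol show that French patients would be counted twice. It does say "Ultimately, 6 data sources from 5 European countries were included in the study", two of them French, but Table 1 has a single French column, Table 4 counts France once, and nothing says that six sources will be summed.

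**What to change.** In section 6.7.1, commit to a pooled estimate for each AESI category that does not depend on events per source and keeps sources with no events. One way is summed events over summed patients, or over summed person-time for rates, with an exact confidence interval, subject to custodian rules on aggregating small counts. Show it beside the source-level results, and state in section 6.7.2 that this is what the overall study population means.

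In section 6.5 and the abstract, replace the ±1 statement with exact limits: 0.27% to 2.54% for 4/400, 2.30% to 6.41% for 16/400, and an upper limit of 0.92% for 0/400. Add the precision expected at source-level sizes. If a pooled estimate cannot be committed to, withdraw the pooled precision claim and state source-level precision only.

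The cost is text in sections 6.5, 6.7.1 and 6.7.2 and the abstract, plus agreement with the data custodians on aggregation. The stated precision becomes slightly less favourable. No extra data are needed.
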